OBSP	On Blinded Study Product
PYR	Person-Years
SDMC	Statistics and Data Management Center
SAE	Serious Adverse Event
SMC	Study Monitoring Committee
SOC	System Organ Class
TDF	tenofovir disoproxil fumarate
TDF/FTC	tenofovir/emtricitabine (trade name: Truvada®)
TFV	tenofovir
TFV-DP	tenofovir diphosphate

1. INTRODUCTION

This statistical analysis plan (SAP) details the statistical procedures that address the primary study objectives specified in Version 2.0 of Protocol HPTN 084 (dated: 6 November 2019): ***A Phase 3 Double Blind Safety and Efficacy Study of Long-Acting Injectable Cabotegravir Compared to Daily Oral TDF/FTC for Pre-Exposure Prophylaxis in HIV-Uninfected Women***. Any meaningful changes or additions to this SAP (e.g., in response to protocol amendments or violations of assumptions underlying pre-planned analyses), and the timing of such changes in relation to unblinding of statisticians performing the analyses, will be documented in a designated section of the SAP. New versions of the SAP will be issued to document updates and changes in the plan. Analysis plans for sub-studies not addressed in the protocol, and for secondary analyses not anticipated prior to study completion, and for exploratory analyses will be developed as separate documents.

Plans for formal interim analysis of trial data are outlined in Section 7.2. A more detailed plan is documented separately in HPTN 084 Interim Monitoring Guidelines. Any substantive modifications to analysis methods or type I error control made in response to DSMB reviews or changes in the protocol will be documented in subsequent versions of the SAP. In DSMB reviews, the HPTN Statistical and Data Management Center (SDMC) will routinely report on operational metrics (e.g., rates of recruitment, retention, study drug discontinuation). These reports are also routinely shared with the study sites to monitor operational performance based on these metrics.

2. GENERAL DESIGN CONSIDERATIONS

2.1 Purpose:

To evaluate the safety and efficacy of the injectable agent, cabotegravir (CAB LA) compared to daily oral tenofovir disoproxil fumarate/emtricitabine (TDF/FTC), for pre-exposure prophylaxis (PrEP) in HIV-uninfected women.

2.2 Design:

Multi-site, double blind, two-arm, randomized (1:1), controlled superiority trial of the safety and efficacy of CAB LA compared to daily oral TDF/FTC for HIV prevention.

2.3 Population:

HIV-uninfected women at risk for acquiring HIV, 18 to 45 years old.

2.4 Study Size:

The original sample size calculation was to enroll 3200 women. In response to a recommendation from the HPTN Study Monitoring Committee in October 2020, this target was increased to 3350 in LOA 3.

2.5 Study Duration:

Approximately 4.6 years total, with individual participants being followed on randomized study product between 1.6 years (for the last enrolling participants) to approximately 3.6 years (for the earliest enrolling participants), and on oral TDF/ FTC for an additional 48 weeks. Accrual will require approximately 2 years.

2.6 Study Sites:

Study sites will be in sub-Saharan Africa (SSA).

2.7 Study Regimen and Follow-up:

Once randomized to one of two arms, participants will move through the following steps (active study products are shown in bold text):

2.7.1. Step 1, Oral Run-in Phase:

Arm A – **Daily oral cabotegravir (CAB)** and oral TDF/FTC placebo for five weeks plus an HIV prevention package including behavioral risk reduction and adherence counseling, provision of condoms.

Arm B – **Daily oral TDF/FTC** and oral CAB placebo for five weeks plus an HIV prevention package including behavioral risk reduction and adherence counseling, provision of condoms.

Individuals who discontinue study participation after receiving oral product in Step 1, but do not receive any study product in Step 2 will be offered the option to be followed annually with HIV testing until study end.

A participant that becomes HIV-infected during Step 1 of the study will permanently discontinue study product, be terminated from the study, and referred for HIV-related care.

2.7.2 Step 2, Injection Phase:

Arm A – **CAB LA** as a single intramuscular [IM] injection at two time-points four weeks apart and every eight weeks thereafter and daily oral TDF/FTC placebo plus an HIV prevention package including behavioral risk reduction and adherence counseling, provision of condoms.

Arm B – **Daily oral TDF/FTC** and IM placebo (matching vehicle, identical volume as active injectable product in Arm A) at two time-points four weeks apart and every eight weeks thereafter plus an HIV prevention package including behavioral risk reduction and adherence counseling, provision of condoms.

Step 2 will continue until the required number of endpoints (114) is reached, estimated to be 81 weeks after enrolling the last participant.

Participants who prematurely discontinue blinded study products during Step 2 (having received at least one injection) for any reason other than HIV infection will be offered to transition to 48 weeks of open-label TDF/FTC followed by annual testing through the duration of step 3.

A participant who becomes HIV-infected during Step 2 of the study will permanently discontinue study product, be placed on immediate suppressive ART, and will be facilitated into locally provided ART, and followed at quarterly intervals for 48 weeks after

their last injection prior to diagnosis of HIV in order to test for safety parameters, as well as CD4 cell count and HIV viral load. After 52 weeks, they will be terminated from the study and transitioned to continued HIV-related care.

2.7.3 Step 3, Follow-up Phase:

Arms A and B – Open-label daily TDF/FTC (in order to cover the pharmacokinetic [PK] tail for Arm A participants) will be provided no later than eight weeks after the last injection visit, for up to 48 weeks plus an HIV prevention package including behavioral risk reduction and adherence counseling, and provision of condoms. Participants will then transition to locally available HIV prevention services, including services for PrEP, if available.

Participants with confirmed HIV infection during Step 3 will have their TDF/FTC stopped and be followed quarterly at least for the duration of Step 3, with possible additional assessments and follow-up to be determined by guidance from members of the HIV alias. Study product will be discontinued and participants will be referred for care.

2.7.4. Pregnancy

A participant with a first positive pregnancy test will temporarily discontinue blinded injections and receive a 4-week supply of open label TDF/FTC and may resume blinded treatment if a second test after 4 weeks indicates that she is not pregnant. All pregnant participants with a confirmed positive pregnancy test (four weeks after the initial pregnancy test) will be unblinded and followed by the study every 12 weeks. Regardless of the randomization assignment or point in the study, all pregnant participants will be placed on open-label TDF/FTC for the duration of the pregnancy. Once pregnancy outcome is reached, and after the participant is not breastfeeding, she may resume study product, according to original randomized arm but open-label, and resume visits per the study schedule.

If participants decline to use an approved contraceptive method, they will be given open-label TDF/FTC for 48 weeks starting no later than eight weeks after her last CAB LA/placebo injection. If study follow-up is ongoing she will be required to be followed up at least annually for HIV testing thereafter. If a participant transitioned to open-label TDF/FTC during Step 2, either because she wanted to become pregnant or declined to continue using long-acting contraception, and subsequently changes her mind she may continue in the study on blinded study product (per original randomization) once she has documentation of a negative pregnancy test and of resuming long-acting contraception.

3. STUDY OBJECTIVES

3.1. Primary Objective:

- **Efficacy:** To evaluate the relative efficacy of oral CAB/CAB LA (oral run-in and injections, Steps 1 and 2) vs. daily oral TDF/FTC for HIV prevention (Steps 1 and 2).
- **Safety:** To evaluate the relative safety of oral CAB/CAB LA (oral run-in and injections, Steps 1 and 2) vs. daily oral TDF/FTC for HIV prevention (Steps 1 and 2).

3.2. Secondary Objectives:

- To compare HIV incidence among participants receiving oral CAB/CAB LA vs. daily oral TDF/FTC (Steps 1, 2 and 3).
- To evaluate relative efficacy of oral CAB/CAB LA vs. oral TDF/FTC in subgroups defined by the baseline factors of age, herpes simplex virus-2 (HSV-2) serostatus, contraceptive method, and body mass index (BMI).
- To describe and model the relationship between HIV incidence and drug concentration, within each arm.
- To describe the distribution and correlates of drug concentration, within each arm.
- To compare the acceptability of and preferences for CAB LA vs. oral TDF/FTC.

3.3. Tertiary Objectives:

- To estimate sexual risk behaviors, as measured by self-report and rates of incident sexually transmitted infections (STIs).
- To compare Grade >2 adverse event (AE) rates in women with baseline BMI $</\geq 30 \text{ kg/m}^2$, within each study arm.
- To compare differences in weight gain and BMI, by arm.
- To compare pregnancy incidence and outcomes between arms.
- To evaluate rates of HIV drug resistance among participants who acquire HIV infection during the study among participants receiving oral CAB/CAB LA vs. oral TDF/FTC.
- To determine plasma concentrations of medroxyprogesterone (DMPA) or norethisterone (NET-EN) or etonogestrel when co-administered with CAB LA.

4. STATISTICAL CONSIDERATIONS

4.1 Sample Size and Power

The primary analysis will be based on HIV incidence during Steps 1 and 2. As described previously, we assume that participants will be followed between 81 (latest enrollees) and 185 (earliest enrollees) weeks in Steps 1 and 2 (1.6 – 3.6 years), with a uniform distribution of enrollments over a two-year period. Thus, average time in Steps 1 and 2 will be 133 weeks (2.6 years). Sample size calculations are based on the following assumptions:

- Background HIV incidence, in the absence of any PrEP, is 3.5% per year
- Both CAB LA and TDF/FTC are 85% effective when used with 100% adherence
- 2.5% one-sided type I error rate and 90% power at the indicated alternative
- Average follow-up duration of 2.6 years (range: 1.6 – 3.6 years)
- Maximum 5% lost-to-follow-up per year

Table 4.1 presents five scenarios and associated total sample sizes. All are superiority designs. The first scenario assumes that adherence to TDF/FTC and CAB/CAB LA will be 50% and 85%, respectively, averaged over the entire Step 1 and 2 follow-up period. The second and third scenarios assume a higher adherence to TDF/FTC (second line) and lower adherence to CAB LA (80%) (third line) (these scenarios are considered unlikely). The last two scenarios retain the conservative assumption of 80% adherence to CAB LA and assume lower adherence to TDF/FTC of 45% and 48%. The largest blinded trials of TDF/FTC among women in a similar setting have shown even lower adherence than assumed in Table 4.1.

Given this history we believe that a sample size of at least 3,128 (111 events for a fixed sample size trial; we will target 114 events to allow for interim monitoring) provides an adequate degree of robustness against uncertainties in adherence rates to the two drug regimens. The trial will continue until we reach 114 events, or a stopping boundary is crossed (see below).

Table 4.1. Five Case Scenarios

Adherence		HIV Incidence (%/year) ¹				
TDF/FTC	CAB LA	TDF/FTC	CAB LA	RR	Number Events	Sample Size
.50	.85	2.01	0.97	.48	78	2352
.55	.85	1.86	0.97	.52	98	3112
.50	.80	2.01	1.12	.56	125	3590
.48	.80	2.07	1.12	.54	111	3128
.45	.80	2.16	1.12	.52	98	2686

¹Background incidence is reduced by a weighted average of fully adherent and non-adherent individuals e.g. 2.01 = $3.5 * ((1 - .85) * .5 + 1 * (1 - .5))$

This study will be monitored by a NIAID DSMB, which will meet at least annually to review safety and efficacy data, as well as data quality. The DSMB will use an **O'Brien-Fleming boundary** to consider stopping the trial early for efficacy.

4.1.1 Sample Size Calculation and Monitoring for Efficacy and Harm

Table 1 reviews the key sample size assumptions. We propose five analyses of the 084 data (four interim and one final). Figure 1 shows the times of the interim analyses and the expected accumulation of participants and information (HIV events) over the course of the trial (assuming a constant incidence). The times of the interim analyses are chosen to correspond to the times of the DSMB reviews (every six months). No interim analyses are proposed prior to 1.5 years because of the small amount of information (HIV events) expected early in the trial. The software nTerim 3.0 was used for calculations.

Table 1. Key sample size calculation parameters and results. EOS = end of steps 1 and 2.

Parameter	Value	Comment
Test Significance level, α (2 sided)	0.05	
Average duration of follow-up	133 wks	$(81 + 185)/2$
Proportion uninfected at EOS, Cab	.9718	$\text{Exp}(-.0112 * 133/52)$ (1.12%/yr incidence)
Proportion uninfected at EOS, TDF/FTC	.9484	$\text{Exp}(-.0207 * 133/52)$ (2.07%/yr incidence)
Hazard ratio	.54	Assuming constant hazard in each arm
Power	90%	

Number of events	114	Slightly inflated from fixed sample size 111 due to interim monitoring
Total sample size	3257	2834/.87 where overall retention = .87
Interim monitoring times (expressed as % information)	.22, .39, .59, .78, 1	Corresponds to 6-month intervals, starting at 1.5 years

Figure 1. Planned accumulation of sample size and statistical information, along with proposed times of interim analyses, based on HPTN 084 study design.

[figure not shown]

Table 2 provides detailed information on monitoring the trial for early stopping at the interim analyses. The O'Brien-Fleming spending function is used to determine stopping boundaries. By the time of the first or second analysis we should have a better understanding of enrollment rates and HIV incidence; the timing of the final 3-4 analyses may be modified at that time. Any modifications, if needed, will use the O'Brien-Fleming spending function applied to the cumulative information available at the time of the analysis.

Table 2. Interim analysis plan for monitoring HPTN 084 based on expected accrual and HIV incidence rates. Ho: RR = 1; Ha RR = .54. Type I error rates (a) in the table are for 2-sided tests.

Time (years)	% Information	Expected no. events	Efficacy boundary (Z)	Harm boundary (Z)	Efficacy boundary (RR) [#]	Nominal α	Cumulative α	Cumulative Stop Prob. under Ha
1.5*	22	25.3	-4.64	4.64	.04	.000001	.000001	0.1
2.0	39	44.8	-3.40	3.40	.30	.00066	.00066	8.7
2.5	59	67.0	-2.70	2.70	.50	.00682	.00704	42.7
3.0	78	89.2	-2.32	2.32	.60	.02010	.0223	72.2
3.56	100	114	-2.02	2.02	.68	.0429	.05	90.0

* Removing the first interim analysis has virtually no effect on the boundaries at subsequent times

RR boundary = (#events Cab/# events TDF), conditional on expected number of events; these RR correspond to approximately 1, 10, 22, 33, 46 events in the CAB arm, respectively

4.2 Randomization

Participants will be randomized to one of two study arms in a 1:1 ratio. Randomization will be stratified by study site, and a permuted blocks design will be used to ensure balanced treatment assignments within study site. The randomization scheme will be generated, operationalized and maintained by the HPTN Statistics and Data Management Center.

4.3 Blinding

Study site staff, except for the site Pharmacist of Record or their designee, and participants will be blinded to the random assignments. Blinding will be maintained until the trial is completed or stopped, i.e., the trial is stopped early, or the required number of endpoints (114) has been met. At a specified time directed by the HPTN Statistics and Data Management Center, participants will be notified of their treatment assignment.

In addition, as described in sections 5.14 and 5.18 of the HPTN Protocol 084, v2.0, participants with a confirmed pregnancy will be unblinded. Participants who are unblinded due to pregnancy may restart open-label study product in their original randomization arm (open label CAB LA or TDF/FTC) following delivery and cessation of breastfeeding.

4.4 Accrual and Retention

Approximately 3,350 participants will be enrolled in approximately 24 months and followed through Steps 1 and 2 for 1.6 to 3.6 years and on oral TDF/ FTC for an additional 48 weeks. An average annual retention rate of at least 95% percent will be targeted (87 - 88% for the entire Step 1 and 2 follow-up period).

5. PROTOCOL DEVIATIONS

All protocol deviations will be reported and reviewed on a regular basis, and each case will be managed clinically and with regards to ongoing product administration by the CMC and DAIDS MOs during the course of the trial. Certain serious protocol deviations, identified during the blinded review, may warrant the exclusion of participants from the ITT or Per-Protocol analysis (guidance for adjudication for these deviations is provided in the HPTN 084 Deviation Adjudication Terms of Reference document). Generally, exclusions from the mITT analysis are expected to be limited to participants deemed inappropriately enrolled and resulting in termination from the study. Any exclusion must be carefully adjudicated and scientifically justified prior to breaking the blind for individuals involved in the adjudication process.

6. ANALYSIS POPULATIONS

6.1 Randomized Population

All participants who were randomized

6.2 Intent to Treat (ITT) Population

All participants who were randomized, excluding those who were subsequently found to be inappropriately enrolled due to violations of the inclusion/exclusion criteria that were deemed to warrant exclusion by the adjudication committee.

6.3 Modified ITT (mITT) Population

All women who are included in the ITT Population and who were not HIV infected at enrollment are included in the mITT population.

6.4 Per-Protocol (PP) Population

The mITT population excluding all participants with protocol violations that were determined by the protocol deviation adjudication committee to be exclusionary from the per-protocol population.

6.5 Injection (Step 2) Efficacy Population

The mITT population who receive at least one injection and are uninfected at the time of the first injection, and had at least one follow-up visit with HIV status determined after the first injection.

6.6 Safety Population (Primary Safety)

All ITT participants who received any oral or injectable product.

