6.7 Injection (Step 2) Safety Population

All Safety Population participants who receive at least one injection

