Laboratory results will be summarized by scheduled study visit. Summary calculations such as maximum post-baseline level will include data from interim (unscheduled visits). Formal comparisons of laboratory findings between arms will not be included in the CSR.

- **Adverse Events**

The reporting of safety data is descriptive and will include all subjects who receive at least one dose of investigational product. AEs will be summarized based on the frequency of AEs and their severity for all treated subjects. All AEs will be coded using Medical Dictionary for Regulatory Activities (MedDRA) and summarized by treatment group. Data will be summarized using preferred term and primary system organ class.

If a subject experiences multiple events that map to a single preferred term, the greatest severity will be assigned to the preferred term for the appropriate summaries.

Summaries of AEs will include any AEs reported beginning with the first dose of investigational product on Day 1. The occurrence of adverse events will be summarized by treatment group using preferred terms, system organ classifications, and severity. Separate summaries of serious adverse events, adverse events related to investigational product, and events leading to the discontinuation of investigational product will be generated. All adverse events reported will be listed for individual subjects showing both verbatim and preferred terms.

- **Efficacy and Efficacy Subgroups**

In the Clinical Study Report, primary efficacy analysis will be presented as described in Section 7.3.1. For subgroup analyses, the age and BMI subgroup analyses will be presented in the Clinical Study Report, but analyses considering contraceptive use and HSV-2 status at baseline will not be presented in the Clinical Study Report.

10. Summary of changes

10.1 Version 3.0 was prepared during the planning process for the Clinical Study Report. The blinded statistician continued to not have access to individual level data.

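### The safety population is a subset of ITT, so women who were dosed but later adjudicated out for eligibility leave the primary safety comparison, while SAP 9.2 promises all dosed women

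*SAP*

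**What the plan says.** Section 6.6 sets the Safety Population as "All ITT participants who received any oral or injectable product". Section 6.7 builds the Step 2 set on it: "All Safety Population participants who receive at least one injection".

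The ITT population in 6.2 is not all randomized women. It is the randomized set "excluding those who were subsequently found to be inappropriately enrolled due to violations of the inclusion/exclusion criteria", limited to "violations of the inclusion/exclusion criteria that were deemed to warrant exclusion by the adjudication committee". Section 5 foresees such removals, saying that certain serious deviations "may warrant the exclusion of participants from the ITT or Per-Protocol analysis".

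Section 9.2, under Adverse Events, describes a different set: "The reporting of safety data is descriptive and will include all subjects who receive at least one dose of investigational product". It then repeats the rule: "AEs will be summarized based on the frequency of AEs and their severity for all treated subjects". Neither sentence mentions ITT or makes an exception for adjudicated exclusions.

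**The concern.** An eligibility failure can be a reason to leave a woman out of an efficacy estimate. It is not a reason to leave her out of a safety estimate: she was exposed, and whatever happened to her was observed. Tying the safety set to ITT carries an efficacy-type exclusion into the primary safety comparison.

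Two things are at stake. First, the exposure and events of dosed women can vanish from the safety rates and summary counts. Depending on which criterion was violated, these may be women in whom a harm would be particularly informative. Second, 6.6 and 9.2 can give different denominators for what looks like the same safety population. Section 10.2 says Version 4.0 was prepared for Clinical Study Report programming, so a programmer has to pick one reading with no rule in the SAP to decide it.

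**Working it through.** The SAP has no figure to reproduce here. The check is a comparison of set definitions.

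**Inputs**

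- Randomized population (6.1): all randomized women. Call it R.
- Adjudicated enrollment exclusions (6.2): call it X. Membership depends on the eligibility violation and the committee's decision, not on whether product was taken.
- Women who received any oral or injectable product: call it D.

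**The two safety sets**

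| Source | Set |
|---|---|
| 6.2 ITT | R minus X |
| 6.6 Safety Population | (R minus X) and D |
| 6.7 Step 2 Safety Population | members of the 6.6 set with at least one injection |
| 9.2 Adverse Events | D |

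Since only randomized women are assigned product, D lies within R. The 9.2 set minus the 6.6 set is therefore (X and D): women who were dosed and then adjudicated out of ITT. The sets agree only if no such woman exists.

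**Where the restriction travels**

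- The primary safety analysis (7.3.2), Step 1 adverse events (7.3.3) and laboratory evaluations (7.3.5) use the 6.6 set.
- The Step 2 OBSP adverse event analysis (7.3.4) uses the 6.7 set.
- The tertiary analyses of adverse events by BMI and of weight gain (7.3.7 b and c) use the 6.6 set.

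**Can (X and D) be non-empty?** The SAP allows for it. Oral product is the first step of the regimen (2.7.1), so a woman found ineligible later may already have taken it. Section 5 expects exclusions to concern women inappropriately enrolled and then terminated from the study. Appendix C lists an enrollment error among the reasons for treatment discontinuation, which shows that errors discovered after product assignment are anticipated. It does not show that such women were adjudicated out of ITT.

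**Who is not affected.** Only violations judged exclusionary remove a woman from ITT. Women found to have been HIV-infected at randomization are still counted as ITT participants in 6.16, so that finding alone does not take them out of the safety set.

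**Size, for illustration only.** With planned enrollment of 3,350 (4.4) and an assumed share of randomized women who were both dosed and excluded:

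- 0.1%: 3,350 × 0.001 = 3.35, about 3 women
- 1%: 3,350 × 0.01 = 33.5, about 34 women
- 2%: 3,350 × 0.02 = 67 women

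A few women, or a few dozen, hardly change the rate of grade 2 or higher events, which is the pre-specified primary safety comparison. For deaths, SAEs or a rare event of special interest, one woman can be the difference between an event appearing in a table and not appearing.

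**The case against.** The best defence is that the two sections serve different purposes. Section 6.6 governs the named analyses in 7.3, while 9.2 is explicitly descriptive and names no analysis population; 7.3.2 itself promises further descriptive safety analyses. On that reading the formal comparison runs on the 6.6 set and the report's descriptive tables on all treated women, with no contradiction.

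Other outputs also limit the loss. Section 9.2 provides by-subject listings of deaths, SAEs and events leading to discontinuation, and a listing of all reported adverse events. Sections 7.2.4 and 9.1 give the DSMB a list of adverse events and an SAE listing. None carries an ITT condition, so a serious event in an excluded woman should still be seen. Section 5 requires each exclusion to be adjudicated and justified before the adjudicators are unblinded, which guards against selective removal by arm. The number affected is unknown and probably small.

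Much of this stands as a limit on the impact. The listings mean that such an event would not be hidden, and blinded adjudication protects against biased selection. But a listing does not put a woman back into the numerator or denominator of the 7.3.2 rates or of any summary based on 6.6. The two-purpose reading is also not written down: the SAP nowhere says that the descriptive tables use a wider set than the formal comparison. Even if it did, it would leave unanswered why the formal comparison should omit exposed women.

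**Conclusion.** The concern holds. As written, 6.6 excludes dosed women on eligibility grounds, 9.2 includes them, and the SAP does not reconcile the two. This follows from the definitions and rests on no numerical assumption.

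The size of the consequence is conditional. It is zero if no dosed woman is adjudicated out of ITT. Under an assumed share of 0.1% to 1% it is about 3 to 34 women, for which the SAP offers neither support nor contradiction. The primary grade 2 or higher comparison would barely move; the exposure is in summary counts of rare and serious events and in mismatched denominators. The point should be corrected, but it does not threaten the main safety conclusion.

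**What to change.** - **6.6:** define the Safety Population as all randomized women who received any oral or injectable study product, regardless of exclusion from ITT.
- **6.7:** no separate change; it follows from 6.6. The analyses in 7.3.2 to 7.3.5 and 7.3.7 b and c, which call these populations by name, follow too.
- **9.2, Adverse Events:** name the Safety Population of 6.6 as the reporting set, so that the report's tables and the primary comparison share one denominator.
- **Disposition table in 9.2:** give, by arm, the number of women who were dosed but excluded from ITT, so that the reader can see the size of the difference.
- **Section 10:** record the change and its timing relative to unblinding, as section 1 requires.

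The cost is SAP wording and an updated population flag in the programming. The efficacy populations, type I error and sample size are untouched.
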